3. Currently using illegal drugs (e.g., cocaine, methamphetamine, opiates) (safety risk and potential confounding)
4. Current smoker who does not agree to stop (confounding)
5. Participation in routine (>1 x/week) exercise program (may improve glucose metabolism/vascular function)
6. History of heart disease, orthopedic, metabolic or neurological condition that would contraindicate exercise (safety risk)

Inclusion of Women and Minorities

Women and members of all races and ethnic groups are eligible for this trial. Men are not eligible.

7.c Subject Recruitment Plans and Consent Process

Participants will be recruited from the Center of Women's Health at Washington University School of Medicine/Barnes Jewish Hospital. All obese (BMI \geq 30) patients with on-going pregnancies will be approached for study participation at the first visit in the the trained clinical research coordinator. Patients will be approached through direct personal recruitment through the clinic and consented.

7.d Early Withdrawal of Subjects

Research participation will occur on three separate visits. Participants will be withdrawn if they are unable to complete the procedures during any of the research visits.

7.e Data Collection and Follow-up for Withdrawn Subjects

There will be no follow up of withdrawn participants.

D Study Procedures

D1 Screening for Eligibility

Pregnant women with obesity: Eligibility criteria of patients attending the Center of Women's Health at Washington University School of Medicine/Barnes Jewish Hospital will be reviewed by [name] and by the research coordinator.

D2 Visit 1

These procedures will be performed on over 3 visits separated by \geq 4 days. Participants will be studied within gestation weeks 23-30. The evening before the study visits, participants will consume a standardized meal consisting of 55% carbohydrate, 30% fat, and 15% protein provided by the WUSM Bio-Nutrition Facility. The following morning, fasted participants (10 hrs) will be admitted to the Clinical Translational Research Unit of the Institute of Clinical and Translational Sciences at Washington University School of Medicine (WUSM CTRU) at 8:00 am. Maternal weight (calibrated scale) and height (stadiometer) will be measured.

Body Composition Measurement: Whole-body fat will be quantified using through skin-fold anthropometry (Harpenden, West Sussex, UK).

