Assessment of Laboratory Clinical Variables: Venous blood will be collected from the participants to assess 1) CBC, 2) HbA1C, 3) complete metabolic panel, and blood hormone/metabolites including plasma glucose, insulin, c-peptide, free fatty acid, placental growth factor and vascular endothelial growth factor (VEGF).

The participant will quietly lie in bed for 45 minutes.

Immediately following the 45-minute rest period:

Assessment of Laboratory Clinical Variables: Venous blood will be collected from the participants to assess 1) CBC, 2) HbA1C, 3) complete metabolic panel, and blood hormone/metabolites including plasma glucose, insulin, c-peptide, free fatty acid, placental growth factor and vascular endothelial growth factor (VEGF).

Assessment of Vascular Function

Endothelial Function: Reactive hyperemia peripheral tonometry (RHPT, EndoPAT2000, Itamar Medical, Caesarea, Israel) will be measured before, and immediately post-exercise to assess digital pulse volume responses to arterial occlusion (blood pressure cuff). Briefly, the participant is placed in a sitting position and two disposable, inflatable probes are placed on the index fingers. Following 10 min of baseline signal recording, a blood pressure cuff is inflated for 3-min and following release, the hyperemic response is recorded for 5-min. The EndoPAT 2000 has good reproducibility (ICC=0.74) and has been validated as a measure of endothelial function with an 82% sensitivity and 77% specificity to diagnose coronary endothelial dysfunction⁵².

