Acute Aerobic Exercise or Resistance Exercise Session

Visit # 2 will consist of either: A) a 45-minute aerobic exercise (AE) session on a recumbent cycle ergometer at 70% $VO_{2\text{peak}}$, or B): a 45-minute resistance exercise (RE) session. The RE session will consist of 3 sets of 8-10 repetitions at their 10RM load according to the Adult NIH Molecular Transducers of Physical Activity in Humans (MoTrPAC) Study Protocol: <https://www.motrpac.org/protocols.cfm>. The acute RE session will be individualized, based on the measurements taken from a 10RM (measured without Valsalva maneuver) tests during Visit #1 for 1) knee extension, 2) knee flexion, 3) leg press (i.e. hip and knee extension), 4) ankle plantar flexion, 5) chest press, 6) seated row, 7) bicep curl (elbow flexion), and 8) overhead press. For each exercise, 3 sets of 8-10 repetitions will be performed with a 2-minute rest in between

sets. A 3-second contraction duration for the concentric and a 3-second contraction duration for the eccentric phase of the lift will be targeted. Fasting blood samples will be taken at pre-AE/RE/rest, at 20-min during AE/RE, immediately post-AE/RE/rest, and 60-min post AE/RE/rest as per MoTrPAC protocol. All visits will be separated by 1 week and rest, AE and RE visit order will be randomized through a computerized randomization program. The study scheme is presented in the Figure.

Assessment of Glucose Metabolism

At 60-min following the completion of AE/RE, a 2-hr oral OGTT will be conducted as described in Visit 1.

Assessment of Vascular Function

Endothelial and large artery function testing will be performed as described in Visit 1.

D3 Visit 3

The evening before the study visit #3, participants will consume a standardized meal consisting of 55% carbohydrate, 30% fat, and 15% protein provided by the WUSM Bio-Nutrition Facility. The following morning, fasted participants (10 hrs) will be admitted to the WUSM CTRU at 7:00 am. Maternal weight (calibrated scale) and height (stadiometer) will be measured.

Acute Aerobic Exercise or Resistance Exercise Session

Visit # 3 will consist of either: A) a 40-minute aerobic exercise (AE) session on a recumbent cycle ergometer at 70% VO_{2peak} , or B): a 40-minute resistance exercise (RE) session as described above.

Assessment of Glucose Metabolism

At 60-min following the completion of AE/RE, a 2-hr oral OGTT will be conducted as described in Visit 1.

Assessment of Vascular Function

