The primary objective of this pilot grant is to obtain preliminary data necessary for proof-of-concept and for sample size estimation for a large, multisite clinical trial. However, we anticipate having enough power to demonstrate independent acute effects of AE and RE on glucose metabolism and vascular function necessary for potential publication of these pilot data. Using data from non-gravid adults with obesity, Newsom et al.⁵⁸ demonstrated an increase in next day insulin sensitivity following a low-intensity AE session. Rynders et al.⁵⁹ found lower 2-hr OGTT glucose value following acute AE in prediabetic non-gravid adults. Further, Breen et al.⁶⁰ demonstrated a 17% improvement in glucose AUC following acute RE in normoglycemic non-gravid adults. Using these data, a sample size of n=14 would be adequate to see a statistical difference with either acute AE or RE on glucose metabolism. For vascular function, Haynes et al.⁶¹ demonstrated increased (~4-12%) reactive hyperemic responses following acute RE and AE in older men. Also, Kingsley and Figueroa⁶² found increased reactive hyperemic responses following acute RE in 24 obese older women. These data suggest that a sample size of n=11 will be necessary to see statistically significant differences in vascular function pre/post acute AE or RE, assuming similar responses.

F2 Statistical Methods

We plan to assess differences in glucose metabolism and vascular function between the three different conditions (i.e. acute, AE, RE) using a repeated measures ANOVA with post-hoc testing. We anticipate detecting differences between AE/RE and rest but likely will not have the power to detect potential differences between AE and RE. The two primary outcomes will be the Matsuda ISI and endothelial hyperemic response (digital pulse volume). Other glucose metabolism and plasma analyte variables will be secondary outcomes.

G Study Monitoring, Auditing, and Inspecting

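### Sections 7.d, 7.e and F2 do not say how a withdrawn woman's completed sessions are used, and the classical repeated measures ANOVA excludes her; a mixed model would keep them

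*Combined protocol and SAP*

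**What the plan says.** Section 7.d: "Participants will be withdrawn if they are unable to complete the procedures during any of the research visits". The heading of 7.e covers data collection as well as follow-up, but its only sentence is "There will be no follow up of withdrawn participants". It does not say whether measurements taken before withdrawal are kept or analysed.

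F2 compares the three conditions "using a repeated measures ANOVA with post-hoc testing". It defines neither the post-hoc tests nor an analysis set nor the handling of a missing condition. It does name the comparison it relies on: "We anticipate detecting differences between AE/RE and rest". It expects too little power for aerobic (AE) against resistance (RE) exercise.

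C6 gives 15 women; nothing says whether that means enrolled or completed. F1 states that "a sample size of n=14 would be adequate to see a statistical difference with either acute AE or RE on glucose metabolism" and that "These data suggest that a sample size of n=11 will be necessary to see statistically significant differences in vascular function". The second sentence goes on to define its difference as before against after an exercise session.

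Visit order is described in two ways. D2 puts the rest condition at Visit 1 ("The participant will quietly lie in bed for 45 minutes"), and the two D3 sections give Visits 2 and 3 to exercise. Yet D3 Visit 2 also says that "rest, AE and RE visit order will be randomized through a computerized randomization program".

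**The concern.** A classical repeated measures ANOVA needs a value in every condition for every woman. A woman who completes rest and one exercise session and is then withdrawn has a complete pair for a contrast the study relies on, but the overall test cannot use her. Whether the contrast uses her depends on how the post-hoc tests are run, which is left open.

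F1 gives the pilot's purpose as proof of concept and the sizing of a larger trial. With 15 women, completed sessions should not be set aside when a standard method can use them, and the choice should be made before the data are seen.

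**Working it through.** **The plan's own figure.** F1 gives no alpha, sidedness, power or standard deviation, so n=14 cannot be reproduced. For a paired t test at two-sided 0.05 (assumed), n=14 implies a standardised paired difference dz of 0.810 if 80% power was meant, or 0.938 if 90%.

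**Does the classical method exclude her?** On simulated data for 15 women and 3 conditions with one value missing, a standard repeated measures ANOVA routine refused the data as unbalanced. It ran only after her removal, with error df (14−1)×(3−1) = 26. A random-intercept mixed model used 44 observations from all 15 women.

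**Does the question arise?** The chance that at least one of 15 women is lost is 1−(1−p)^15. For assumed p of 5, 10, 15 and 20% this is 0.54, 0.79, 0.91 and 0.96. These figures say how often the question comes up, not how much harm follows.

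**Precision.** Assumptions: 15 enrolled without replacement, k lost, equal variances, within-woman correlation ρ from 0.5 to 0.85, rest at Visit 1, and AE or RE first with probability 0.5.

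- Completers only: Var(AE−rest) = 2σ²(1−ρ)/(15−k).
- Mixed model: Var = c′I⁻¹c, where I sums each woman's information from the conditions she has and c = (−1, 1, 0) over rest, AE, RE.
- Example with ρ=0.5, σ²=1, k=3. Completers: 2×0.5/12 = 0.0833. If two partial women have AE and one has RE, the mixed model gives 0.0698 for AE−rest and 0.0735 for RE−rest. The standard error ratios are √(0.0698/0.0833) = 0.915 and √(0.0735/0.0833) = 0.939.
- Available pairs: the ratio is √((15−k)/(15−k+j)), averaged over j ~ Binomial(k, 0.5). For k=3: (1/8)×1 + (3/8)√(12/13) + (3/8)√(12/14) + (1/8)√(12/15) = 0.944.

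Standard error relative to completers only:

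| Lost | Mixed model, lost at Visit 3 | Available pairs, lost at Visit 3 | Mixed model, lost at Visit 2 (rest only) |
|---|---|---|---|
| 1 | 0.978–0.979 | 0.983 | 0.992–0.998 |
| 2 | 0.954–0.956 | 0.965 | 0.983–0.995 |
| 3 | 0.928–0.931 | 0.944 | 0.975–0.992 |

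At ρ=0.7, available pairs recover 0.017/0.022 = 77%, 0.035/0.045 = 78% and 0.056/0.070 = 80% of the Visit 3 gain. Across the range of ρ the share is 75 to 81%. For loss at Visit 2 they recover nothing, because she has no pair.

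**Power.** The noncentrality is dz√n/r, where n is the number of completers and r the ratio above, with n−1 degrees of freedom kept throughout. For n=12 and dz=0.810 it is 0.810×√12 = 2.806 for completers and 2.806/0.93 = 3.017 for the mixed model.

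| Lost at Visit 3 | Completers, if n=14 meant 80% | Mixed model | Completers, if n=14 meant 90% | Mixed model |
|---|---|---|---|---|
| 1 | 80.0% | 81.7% | 90.0% | 91.2% |
| 2 | 76.5% | 80.2% | 87.3% | 90.1% |
| 3 | 72.4% | 78.4% | 84.0% | 88.8% |

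With 3 lost at Visit 2, the mixed model gives 73 to 75% (80% case) or 85 to 86% (90% case).

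**Period term.** With rest always at Visit 1, a model with an intercept, two condition terms and two period terms has 5 columns but rank 4. AE−rest and RE−rest are not estimable; AE−RE is. If all three conditions are randomised in order, condition and period can both be fitted. With 3 lost, the mixed-model standard error is then 6 to 7% smaller (Visit 3) or 0.7 to 2.2% smaller (Visit 2) than with completers. The period term raises the completers' standard error by a factor of 1.013.

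**The case against.** F2 does not prescribe complete-case analysis. A reader might infer that the plan drops a withdrawn woman from every contrast. The documents do not support that: the exercise-versus-rest comparisons are the post-hoc tests, F2 does not define them, and paired tests on available pairs would keep her. This stands, and it means that one clarifying sentence would secure most of the Visit 3 gain without changing the method. What remains is her exclusion from the overall test, the rest of the gain, and the fact that the choice is left open.

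A reader might also take n=11 against 15 as room for four losses. That does not follow. F1's n=11 is for a change from before to after a session, and D2 measures the EndoPAT outcome on both occasions, so the figure is not a margin for exercise versus rest. Section 7.d can also be triggered by one unfinished procedure. A woman who cannot finish the glucose test may still have a usable vascular measurement at that visit, so treating the whole visit as missing is itself an assumption.

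Finally, if 15 means completers with replacement, little precision is lost. The documents do not say.

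**Conclusion.** The point holds as a minor one. The plan leaves the use of partial data open, and the named method in its classical form excludes such women from the overall test. For the contrast of interest the avoidable loss is about 2 to 7% of the standard error with 1 to 3 women lost at Visit 3, and at most 2.5% at Visit 2. That is about 2, 4 and 6 points of power for 1, 2 and 3 lost at Visit 3 if n=14 meant 80%. The sizes rest on assumed loss, correlation, alpha and target power. The 6-point case needs 3 of 15 women (20%) lost, all at the last visit.

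It would be too strong to treat 14 of 15 as a threshold below which the study fails: 13 completers still give about 77% power, or 87% if 90% was meant.

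**What to change.** - **7.d/7.e:** state that all data collected before withdrawal are kept and analysed. Who may continue to later visits is left to the sponsor.
- **F2:** replace the repeated measures ANOVA and its post-hoc tests with contrasts from a linear mixed model (REML, condition fixed, random woman effect, small-sample degrees of freedom such as Kenward-Roger) using every available condition. Keep a completer analysis as sensitivity.
- **Period effect:** first reconcile D2 Visit 1 with the randomisation sentence in D3 Visit 2. Add period only if the order of all three conditions is randomised. If rest is always first, fit condition only and report that rest and Visit 1 cannot be separated.
- **Reporting:** give completion and withdrawal by visit, condition and reason, and say in F1 whether 15 is enrolled or completed.

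The cost is wording and a different model, with no added visits or procedures. With complete data the condition-only model gives the same F test as the ANOVA when the estimated between-woman variance is above zero (F=1.313 for both in a simulated check). Under randomised order the period term costs about 1.3% in standard error. The model assumes data are missing at random and does not remove selection towards women who tolerate both sessions. The gain is small if few women are lost.

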Endothelial and large artery function testing will be performed as described in Visit 1.

Plasma Hormone and Metabolites

Before, during and immediately following the rest, AE and RE sessions and during the OGTT, maternal blood will be collected for analyses of plasma glucose insulin, C-peptide, free fatty acid, vascular endothelial growth factor (VEGF), and placental growth factor. Additional blood will be collected for future exploratory analyses (e.g. metabolomic, proteomic, transcriptomic). Plasma glucose will be analyzed by an YSI glucose analyzer (Yellow Springs Instruments, Yellow Springs, OH) located on the WUSM CTRU. Plasma hormone and analyte analyses will be performed by the University of Alabama at Birmingham (UAB) Diabetes Research Center Human Physiology Core Laboratory (see letter of support from [name], Director of Core Laboratory).

MicroRNA Expression

Before, immediately following, and 60-minutes following the rest, AE and RE sessions, maternal blood (6 ml) will be collected for analyses of microRNA (miRNA) expression of peripheral blood mononuclear cells. MicroRNAs are small noncoding ~19–24 nucleotide-(nt-) long RNA molecules that play an important role in the modulation of gene expression. Analysis will be performed using a Affymetrix Gene Chip and will be performed by the Washington University Gene Technology Access Center.

[figure not shown]

Figure: Acute Rest, AE or RE Session Schematic. AE: aerobic exercise, RE: resistance exercise, OGTT: oral glucose tolerance test.

E Safety and Adverse Events

The entities providing oversight of safety and compliance with the protocol require reporting as outlined below.

The Washington University Human Research Protection Office (HRPO) requires all events meeting the definition of unanticipated problem or serious noncompliance be reported as outlined in Section G2.

E1 Definitions

1.a Adverse Events

Definition: any unfavorable medical occurrence in a human subject including any abnormal sign, symptom, or disease. For purposes of this research project, AEs associated with peak exercise testing, 1-repetition maximum testing, aerobic or resistance exercise sessions, blood draw/OGTT, and vascular function testing will be tracked.

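### The text does not clearly schedule a pre-session endothelial reading for the rest condition, and F2 does not say whether the post value or the change is analysed

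*Combined protocol and SAP*

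**What the plan says.** Visit 1 in Section D2 is the rest visit: "The participant will quietly lie in bed for 45 minutes". Ahead of that it lists weight and height, skin-folds ("Whole-body fat will be quantified using through skin-fold anthropometry") and a venous blood draw. The blood draw is listed again after the rest. The vascular assessment appears once, below the line "Immediately following the 45-minute rest period". The RHPT paragraph below that line says the test "will be measured before, and immediately post-exercise to assess digital pulse volume responses to arterial occlusion".

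For Visits 2 and 3 (both numbered D3) the vascular instruction is only: "Endothelial and large artery function testing will be performed as described in Visit 1". Blood is handled differently. The Visit 2 text names time points before and after AE, RE and rest.

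F1 gives n=11 as the number needed to see "statistically significant differences in vascular function pre/post acute AE or RE". F2 names the endothelial hyperemic response as one of two primary outcomes and plans a repeated measures ANOVA across the three conditions, expecting AE and RE to differ from rest. It mentions no change score, pre/post factor or baseline covariate.

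**The concern.** At Visit 1 the timing line and the sentence below it cannot both be followed literally. The line puts RHPT after rest. The sentence asks for a reading before, and one after an exercise bout that has not occurred; the peak exercise test comes only after lunch. Staff who follow the layout would take no pre-rest reading, and that reading cannot be recovered later.

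The control condition for a primary outcome is at stake. If AE and RE have pre and post values and rest has only a post value, the pre/post change that F1 is built on has no matching change under rest. It could then not be set against the effect of time or of repeated cuff occlusion. A same-visit baseline is also useful because the layout puts rest at Visit 1 with admission at 8:00, and exercise at Visits 2 and 3 with admission at 7:00, although the Visit 2 text says the order of all three conditions is randomized. Finally, the pilot is meant to supply sample-size inputs for a larger trial, so the quantity whose variance it estimates has to be defined.

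**Working it through.** **1. What each reading of the schedule allows**

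| Reading | Rest | AE and RE | Consequence |
|---|---|---|---|
| Timing line governs at all visits | post | post | Post-only comparison possible; F1's pre/post contrast unavailable |
| Sentence governs at all visits, with exercise meaning the session | pre, post | pre, post | Every analysis possible |
| Timing line at rest, sentence at exercise visits | post | pre, post | Post-only comparison possible, with unequal prior cuff exposure; change-versus-rest and baseline-adjusted comparisons not possible |

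The third reading is natural because the sentence fits Visits 2 and 3 as it stands, and because blood is listed on both sides of the rest while RHPT is not. The text does not force it.

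**2. The plan's own figure**

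The n=11 in F1 cannot be reproduced, because alpha, power and the SD of change are not stated. Assume two-sided 0.05, 80% power and a paired t-test. Then n=11 corresponds to a standardised change of 0.94. With F1's cited effect of about 4 to 12%, the SD of change would be 4/0.938 = 4.3 to 12.8 percentage points (12/0.938).

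That is a single pre/post change. Set it against an equally variable rest change, uncorrelated across visits (assumed), and the variance doubles: 0.94/√2 = 0.66. Power for the same effect falls from 80% to 51% at n=11, and from 92% to 67% at n=15. Raw change scores are therefore costly even when the rest baseline exists.

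**3. Precision of the three possible analyses**

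Inputs: ICC 0.74 (C3 and D2), read as visit-to-visit (assumption); n=15 (C6); three conditions; k, the correlation of pre and post values within a visit after removing the woman effect (assumed, 0 to 0.75).

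With total variance 1, the within-woman part is s² = 1 − 0.74 = 0.26. Per-woman variance of a contrast between two conditions:

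- post value only: 2s² = 0.52
- raw change: 4s²(1 − k), a ratio to post-only of 2(1 − k)
- post value with a within-woman pre covariate: 2s²(1 − k²), times a factor for estimating the slope. Removing woman and condition leaves (15 − 1)(3 − 1) = 28 degrees of freedom for the pre value, so the factor is 1 + 1/(28 − 2) = 27/26 = 1.038.

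| k | Raw pre/post correlation, 0.74 + 0.26k | Raw change / post-only | Covariate / post-only |
|---|---|---|---|
| 0 | 0.74 | 2.00 | 1.04 |
| 0.25 | 0.805 | 1.50 | 0.97 |
| 0.50 | 0.87 | 1.00 | 0.78 |
| 0.75 | 0.935 | 0.50 | 0.45 |

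A simulation of this model at n=15 with woman as a fixed effect agrees to within 0.01. The ICC cancels from the ratios; it serves only to translate k into the raw correlation. Raw change beats post-only when k exceeds 0.5. The covariate beats post-only when k² exceeds 1/27, that is, k above about 0.19. Raw change overtakes the covariate only when 2 < 1.038(1 + k), that is, k above about 0.93, and then by under 4%.

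The form of the covariate matters. With the uncentred pre value in a random-intercept model, simulated variance relative to post-only is about 1.40, 1.2 and 0.9 at k = 0, 0.25 and 0.5, because one slope then mixes between-woman and within-woman relations.

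**The case against.** The case on the other side has four parts.

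- **The missing rest baseline is not established.** A reader might infer that the plan omits it. The documents do not support that: the third reading applies the timing line at one visit and the sentence at the others. D2 also introduces its procedures as common to three visits, which favours one schedule. The session schematic, captioned for rest, AE and RE together, cannot be seen here and may mark a pre-rest test. This stands. The baseline is unscheduled in the text, not proven absent.
- **Comparison with rest does not depend on a baseline.** A reader might infer that without one, exercise effects cannot be separated from time. In a within-woman design, post values after rest, AE and RE can be compared directly, and the rest session accounts for elapsed time. This stands, apart from unequal prior cuff exposure under the third reading.
- **F2 does not reject the pre value.** It is silent. This stands; the fault is an undefined endpoint.
- **Covariate adjustment is not free in small samples.** This also stands: it loses about 3 to 4% of variance at k=0, and much more if the covariate is entered carelessly.

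None of this reconciles the timing line with the sentence, and no visible passage does so. The variance table compares analyses that assume the readings exist; it does not measure the harm of a missing baseline.

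**Conclusion.** The concern holds in limited form. For a primary outcome, the Visit 1 text conflicts on timing, and the exercise visits inherit the conflict by cross-reference. F1 and F2 do not agree on, or do not state, the quantity analysed. If the Visit 1 timing line is followed, the control condition loses a baseline that the RHPT sentence seems to promise. A change-versus-rest or baseline-adjusted analysis then becomes impossible, although a post-only one survives.

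The gain from using the pre value as a within-woman covariate runs from a loss of about 4% in variance (k=0) to a reduction of about 55% (k=0.75). Raw change runs from double the variance to half. These figures rest on an assumed k, equal variances across conditions and n=15 complete sets of visits. Reading the ICC as visit-to-visit affects only the conversion of k to a raw correlation. The change is worth making, but the trial does not fail without it.

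**What to change.** - **D2 and D3:** list RHPT immediately before and immediately after the rest, AE and RE sessions, with the explicit per-condition time points already used for blood, and make the schematic agree.
- **F2:** define the endpoint as the post-session RHPT value, with that visit's pre-session value as covariate. Enter woman as a fixed effect, or centre the pre value within woman. Do not use raw change scores.
- **F1:** state that n=11 refers to a single pre/post change, and give the alpha, power and SD behind it.

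The cost is protocol wording and one residual degree of freedom. If the pre-rest reading was not already intended, add one non-invasive recording of 10 + 3 + 5 = 18 minutes per woman.
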